Effects of a Numerical Superiority and Inferiority Tactical Training Program Compared to
Conventional Training on Procedural Tactical Knowledge and Executive Functions in
Soccer Players. A Randomized Controlled Trial

Date: September 9th, 2023

Protocol

There is a great need to establish reliable evaluation and intervention protocols to improve the tactical component, decision making (TD) and procedural tactical knowledge (PTK) in Soccer.

Objectives

To determine the effects of a tactical training program of numerical superiority and inferiority during 12 weeks of follow-up on the PTK, which will be evaluated by calculating offensive, defensive and global effectiveness indices (EI) of 24 male amateur soccer players, as well as the effect on their executive functions.

Type of study

The study corresponds to a predominantly quantitative approach. According to Friedman et al., (2010) it is a prospective, experimental study, in parallel, with 2 randomized groups (experimental and control). The study is a repeated measures design because measurements of the most important outcomes (primary and secondary) will be performed at four times: pretest (week 1), intermediate test 1 (week 6), intermediate test 2 (week 11) and posttest (week 16).

Site Selection (Context and Access)

The study is being carried out with soccer players from a club that competes in the Antioquia Soccer League who train on fields in the city of Medellín, which are made of synthetic grass and natural grass. These fields are in good condition and offer adequate technical conditions and security for soccer players.

Population

The investigation is being carried out with amateur soccer players, male, in the First B departmental category.

Selection criteria

Inclusion criteria

Soccer players belonging to a soccer club.

Soccer players playing roles of outfield (all except goalkeepers).

They compete in the First B category of the Antioquia Football League in the 2023 season.

Players aged between 17 and 26 years.

Players with at least six months of experience in federated soccer.

Players who do not present cognitive disorders that make learning difficult, which can be identified through monitoring by the coaches and/or tests carried out by the Neuropsychology staff.

They must be affiliated to the health system of the contributory or subsidized regime.

They must agree to participate in the study after knowing and signing the consent or informed assent as appropriate.

Exclusion criteria

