PTK (IE global)	Dependent	Quantitative	Continuos, Ratio	IE (***)formula)	FOCOS
Executive functions "component" 1	Dependent	Quantitative	Discrete, interval Continuos, Ratio	Number of Hits/Errors Time (sec, min)	Tower of Hanoi
Problem solving "component" 2	Dependent	Quantitative	Discrete, interval	Number of Hits/Errors	Tower of Hanoi

Cognitive flexibility			Continuous, Ratio	Time (sec, min)	
"Component" 3 Impulse control	Dependent	Quantitative	Discrete, interval	Number of Hits/Errors	Stroop test
"component" 4 Visuospatial working memory	Dependent	Quantitative	Discrete, interval	Number of Hits/Errors	Corsi Cubes
"Component" 5 Executive Attention	Dependent	Quantitative	Continuous, Ratio	Time (sec, min)	Trail Making Test (TMT)
"component 6" Sustained attention	Dependent	Quantitative	Discrete, interval	Number of Hits/Errors	Crossing out boxes
			Continuous, Ratio	Time (sec, min)	
Age	Confounding	Quantitative	Continuous, Ratio	Years and months	Survey
Sports age	Confounding	Quantitative	Continuous	Years	Survey
Playing position	Confounding	Qualitative	Nominal	Lateral, Central, Midfielder, Winger, Forward	Survey
Socioeconomic	Confounding	Qualitative	Ordinal	Scale from 1 to 6	Bill of public services of the house
Educational level	Confounding	Qualitative	Ordinal	School grade	Survey
Mass	Confounding	Quantitative	Continuous, Ratio	(kg)	Scale
Height	Independent	Quantitative	Continuous, Ratio	(cm)	Stadiometer
IMC	Confounding	Quantitative	Continuous, Ratio	(kg/m ²)	Equation
Mental fatigue	Confounding	Qualitative	Ordinal	Scale from 0 to 100	Question

Notes:

*Offensive effectiveness indices (IE) = Sum of the IE of the offensive tactical behaviors/Number of categories in which the soccer player developed offensive tactical behaviors.

** Defensive IE = Sum of the IE of the defensive tactical behaviors/N° of categories in which the Soccer players developed defensive tactical behaviors

*** Global IE = Offensive IE + Defensive IE/2

Masking

People who carry out the assessments are masked (they do not know which group the athletes were assigned to). In order to carry out an adequate strategy to control information biases, the professionals who carry out the evaluations are masked (blinding). Consequently, the evaluators of the primary, secondary, and exploratory outcomes were masked as follows:

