PTK (offensive, defensive, and global IE) (expert soccer coach, licensed A soccer coach from the Colombian Federation, video analyst with excellent knowledge and management of videoanalysis's software such as Nacsport and he is an expert of observation categories and trained in the FOCOS (Football Competence Observation System) evaluation instrument, as well as in the management of the LINCE PLUS software).

Executive functions (problem solving, cognitive flexibility, impulse control, visuospatial working memory, executive attention, and sustained attention). These evaluations are developed by the neuropsychologist.

Professional who carry out the anthropometric evaluations is masked, she is researcher with training in sports training and use of scales and height rods.

Person who applies the survey to the soccer players to inquire about the sociodemographic characteristics of the population is masked too.

In the same way, the professional who asking to the research participant are masked too, which inquiries about the level of mental fatigue that they perceive just before the evaluations of executive functions and the FOCOS test.

The evaluations are carried out by expert professionals, with training and experience in each of the areas as described in the previous section, which guarantees their reliability. The evaluators of each of the areas mentioned above only carry out the tests (pretest and posttest) and intermediate tests 1 and 2 for the offensive, defensive, and global IE. These evaluators will report the results to the principal researcher, who in turn will file them on a personal computer with a password so that no one else has access to the information and will make backup copies in the cloud. In this way, this level of the investigation will be masked. Subsequently, the principal researcher will send the data to the statistician to proceed with data processing and information analysis.

In the same way, the statistician who will analyze the data will be masked, in this sense, the statistician will not know the identity of the participants he is analyzing, he will process data from coded subjects. The statistician will also not know to which comparison

group the data of the participants he will analyze belongs. In this way, 2 levels of the study will be masked (evaluators and data analysis).

Ethical aspects

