The guidelines of the Declaration of Helsinki (updated at the 64th general assembly in Fortaleza in 2013) and of the Ministry of Health and Social Protection of Colombia through resolution 8430 of 1993 will be followed. All measures will be provided to guarantee the confidentiality of the data of the participants by assigning codes. All participants and their legal representatives (for minors) were informed of the particularities of the research through informed consent and/or assent regarding exposures, expected results, and contributions to the academic and sports field. The results obtained will be returned to the participants, their relatives and/or legal representatives and the participating soccer club. The endorsement of the research bioethics committee of the Institute of Physical Education and Sport (IUEFD) was obtained (ACEI 39-2023, June 20th, 2023). The present investigation is classified in the category of minimum risk according to article 11 of resolution 8430 of 1993 of the Ministry of Health of Colombia. In any case, the development of this research does not represent an additional risk to the activities, training sessions and competitions in which the soccer players participate daily.

Interventions (GE and GC Training Plans)

GE (Tactical Training in Numerical Superiority and Inferiority)

The participants of the GE will carry out a specific training program, with the objective of improving both offensive and defensive technical and tactical action (ATT) that allow the increase of the IE (offensive and defensive). The formats through which the GE subjects will train are Small Sided Games (SSGs) and ATT 2v1, 3v2 and 4v3, alternating them during the week (SSGs on Tuesdays and ATT on Thursdays). It is important to mention that, in terms of physical demand, the training through these 2v1 and 3v2 formats are similar, and therefore, can be assimilated in part, to those proposed by Casamichana and Castellano (2016) to the SSGs of level 14 and level 16 (on a scale from 1 to 20, with 20 being those with the greatest physical demand), in which the JER of 1v1 and 2v2 present the following specifications: Level 14: 2 series X 6 repetitions X 1'30" of

exercise X 1' 30" pause (total 12 repetitions of SSGs) and Level 16: 2 series X 7 repetitions X 1'30" of exercise X 1'30" of rest (total 14 repetitions of SSGs).

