The characteristics of this training program are training frequency 5 times/week, 1 official competition on weekends, ATT stimulation frequency in 1v1, 2v2 and 3v3 formats is 2 times/week, the specific training time assigned it will be 40 minutes per training session and will be done after the set-up (warm-up). The total volume of the program is 960 minutes. As mentioned above, the coach that will execute the CG training program will be different from the one that will execute the GE training program. As with the provisions of the GE, for the CG a coach will also be assigned to register, quantify, and monitor the training stimuli of this group, who will record it in forms designed for this purpose.

The training sessions, both for the GE and CG, will take place on synthetic and natural grass pitches, which are in good condition to guarantee the normal development of the practices. If for some reason of force majeure, the training session cannot be carried out on the day assigned within the protocol, an attempt will be made to carry it out the following day, that is, Tuesday session would be performed on Wednesday and Thursday session would be performed on Friday, thus guaranteeing the weekly specific stimulation frequency (FEES). The exercises will be carried out with GOLTY N°5 balls.

Information Collection Instruments

To evaluate the primary, secondary, exploratory outcomes and the confounding variables, a battery of tests and protocols will be carried out, which are described below.

PTK (Offensive IE, Defensive IE, Global IE)

The PTK will be evaluated through the FOCOS test. This test evaluates all the actions in attack (21 actions) and all the actions in defense (10 actions) through which the offensive score, defensive score and total score are obtained and with these scores the IE is calculated (offensive, defensive and global) of each participant and each group.

Likewise, strengths, weaknesses, aspects to improve in each tactical behavior and/or phase of play can be determined according to the role (attacker with the ball, attacker without the ball in the center of the play, attacker without the ball outside the center of the play, defender to intervene in space, defender in the center of the play and defender outside the center of the play). Likewise, the actions are evaluated according to the subrole, in attack: ball control, driving, dribbling, passing, shooting, ball circulation and positioning

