To establish the distribution of the data of the quantitative variables, the Shapiro-Wilk test will be applied. The variables that present a normal distribution will be summarized with means and standard deviation. Variables that present a non-normal distribution will be summarized with medians and interquartile ranges. Likewise, the qualitative variables will be presented in absolute and relative frequency tables.

To establish the behavior of the offensive, defensive, and global IE, a repeated measures design will be carried out that includes 4 evaluations over time (pretest, intermediate test 1, intermediate test 2 and posttest). For this, an ANOVA of repeated measures or the Friedman test will be used according to the normality of the variables, in addition, the assumption of homogeneity of the variances will be evaluated based on the Levene statistic. Since different dependent variables will be evaluated, a multivariate analysis of variance (MANOVA) will also be performed.

For the variables related to executive functions, an intragroup analysis of each of the groups (GE and GC) will be carried out, comparing the pretest and posttest values to establish possible differences, for which the dependent student t test or the Wilcoxon test of according to its distribution. In addition, an intergroup analysis will be carried out to compare the possible differences between the groups (GE and GC), for which the student t test for independent samples or the Mann Whitney U test will be applied according to the distribution of the variables. Similarly, confidence intervals (CI95) and two-tailed effect sizes will be reported, with alpha (α) set to 0.05 and statistical power 0.8 (1- β). The statistical significance value is set at $p \leq 0.05$. An analysis of the information will be carried out using the statistical package SPSS version 27 and the software R free version 4.0. Procedures will be carried out to detect possible inconsistencies in the measurements and to identify outliers and extreme values. Likewise, if necessary, statistical adjustments will be made. Intention-to-treat analysis will be performed.

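### Global IE is the natural primary outcome but is never named so, and the three overlapping IEs are each tested at p ≤ 0.05 with no order or multiplicity rule

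*Combined protocol and SAP*

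**What the plan says.** - **Objectives:** PTK is the outcome "which will be evaluated by calculating offensive, defensive and global effectiveness indices (EI". The three indices are listed without rank. Table 1 gives all three the same function (dependent), and the instruments section groups them under "PTK (Offensive IE, Defensive IE, Global IE".
- **Type of study:** "measurements of the most important outcomes (primary and secondary) will be performed at four times". The Masking section likewise says that "the evaluators of the primary, secondary, and exploratory outcomes were masked as follows". Neither says which index has which role.
- **Data Collection Procedures:** FOCOS is said to measure the primary and secondary outcomes, and executive functions are called exploratory. Any ranking of primary against secondary must therefore lie among the three IEs.
- **FOCOS units of measure:** global IE is said to stand for each player's PTK.
- **Table 1 notes:** "Global IE = Offensive IE + Defensive IE/2", so global IE is calculated from the other two.
- **Analysis of data:** "To establish the behavior of the offensive, defensive, and global IE, a repeated measures design will be carried out". The method is repeated-measures ANOVA or Friedman, depending on normality. A MANOVA is added because there are several dependent variables. Significance is p ≤ 0.05. A closing remark allows statistical adjustments where needed, without naming a method or a trigger.

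**The concern.** The protocol uses the vocabulary of a ranked set of outcomes but never assigns the ranks. Three indices, one of them built from the other two, go through the same analysis at the same threshold. As written, nothing stops a report from claiming success on whichever index crosses 0.05. The error rate behind such a claim is the chance that any of three tests is positive, which is above 5%.

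Masking limits this only in part. "The statistician will also not know to which comparison" group the data belong to, so an index cannot easily be chosen because it favours one arm. It can still be chosen by its p-value.

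**Working it through.** **Inputs**
- Two-sided alpha 0.05 (Analysis of data).
- 12 players per group, mean difference 1.13, SD 0.81 (Sample Size Calculation).
- Four occasions (Type of study).
- Global IE taken as the mean of offensive and defensive IE.
- Correlation between offensive and defensive IE: not given, assumed from -0.3 to 0.9. Correlation within a player over time: assumed 0.5.

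**The plan's own figure.** 1.13/0.81 = 1.395 SD. A two-sample t test with 12 per group has noncentrality 1.395 × √(12/2) = 3.417 and 22 degrees of freedom, which gives power 90.4%. This reproduces the 24 players of scenario 3. The section does not tie the 1.13 to any IE. Offensive and defensive IE are averages of success proportions and cannot differ by 1.13, so 1.395 serves below only as a standardised effect.

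**False positives if the three are co-equal.** Data were simulated with no true effect. Each index was tested by the group-by-time F test with 3 and 66 degrees of freedom, counting trials in which any of the three gave p ≤ 0.05.

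| Offensive-defensive correlation | Any of three | Global IE alone |
|---|---|---|
| -0.3 | about 12.4% | about 5% |
| 0 | 12.0% | 5.0% |
| 0.3 | 11.0% | 5.1% |
| 0.5 | 9.9% | 4.9% |
| 0.7 | 8.9% | 5.0% |
| 0.9 | about 7.4% | about 5% |

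A two-sample t test on each index gives nearly the same any-of-three rates: 12.4%, 11.6%, 10.6%, 9.8%, 8.6% and 7.2%. Three independent tests would give 1 - 0.95³ = 14.3%, which overstates the risk because the indices overlap.

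**Power for global IE if only one index moves.** Suppose one index moves by 1.395 SD and the other does not. The mean of the two moves by 1.395/2 = 0.6975, and its SD is √((1 + r)/2), where r is the correlation. The standardised effect is the ratio of these, and the noncentrality is that ratio × √6.

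| r | Standardised effect | Noncentrality | Power (two-sample t) |
|---|---|---|---|
| 0 | 0.986 | 2.416 | 64% |
| 0.3 | 0.865 | 2.119 | 53% |
| 0.5 | 0.805 | 1.973 | 47% |
| 0.7 | 0.757 | 1.853 | 43% |

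If both indices move by 1.395 SD, power for global IE is 94% or more over the same correlations.

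**Why the contrast must be named.** Suppose both indices grow evenly to 1.395 SD at week 16. At correlations 0.7 to 0, simulated power for global IE is about 90% to 99% by the group-by-time interaction. By the group main effect, which averages in the pretest, it is about 61% to 83%. Leaving the contrast open would leave a second choice to be made after the data are seen.

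**The case against.** The best reply is that the hierarchy is already there to be read. FOCOS carries the primary and secondary outcomes, executive functions are exploratory, and global IE stands for PTK, the outcome in the trial's title. On that reading global IE is primary and its test has a 5% error rate. This largely stands. It is why the remedy is a clarification and not a redesign. It does not close the gap, because a reader has to infer the designation. The section on the experimental training points the other way, stating its aim as "improving both offensive and defensive technical and tactical action (ATT) that allow the increase of the IE (offensive and defensive", without mentioning global IE.

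The MANOVA can also be offered as the plan's answer to several outcomes. It is the only response to them in the plan. However, it is described as an additional analysis, not as a test that must be positive before the separate indices are read, so it does not control their joint error. The general remark about adjustments names no multiplicity method.

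A reader might infer that the trial as planned has a false-positive rate of 12%, or of 14.3%. The documents do not support either. The inflation arises only if the three indices are co-equal, the 14.3% assumes independence, and the plan does not spell out the group-by-time test on which the 7% to 12% rests.

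**Conclusion.** The concern holds in a limited form. The documents point to global IE as primary but do not name it, and three overlapping indices are tested at p ≤ 0.05 without order or correction. If they are treated as co-equal, the chance of at least one false positive is about 7% to 12%. This assumes normal data, one group-by-time test per index, and a correlation between 0.9 and -0.3. Further tests by time point or within group would raise it. The Friedman test has no between-group factor, so the figure says nothing about that branch. The omission itself is certain from the text; the size is conditional on these assumptions. Nothing in the documents shows an intention to select among the indices.

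**What to change.** In Analysis of data, state that:
- global IE is the single primary outcome at two-sided 0.05, tested by the group-by-time interaction over the four occasions;
- offensive and defensive IE are secondary, with Holm across the two, and a positive trial cannot be claimed on them alone.

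Record the date of this decision, and make it before post-baseline IE data are analysed. The pretest is described as done, while weeks 6, 11 and 16 are still written as future.

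**Cost.** This is a cheap improvement: a few sentences and a dated note, with 24 players unchanged. The real downside is that, if only one index moves, power for global IE is about 43% to 64% in the case worked above, and that index could be reported only as a secondary result.

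**Left to the sponsor.** This wording holds 5% for the primary claim, not over all three indices. The chance of any false positive, counting global IE and the Holm pair, is 8.2%, 7.4%, 6.7% and 6.2% at correlations 0, 0.3, 0.5 and 0.7. If 5% is to cover all three, there are two options:
- Test the secondaries only after global IE is significant. If one index alone moves, power for it is then 61%, 52%, 47% and 43% at the same correlations.
- Apply Holm over all three with no single primary. Power for that index is then 79% to 80%, against 90% unadjusted, but if both indices move, power for global IE is 88% to 98%, against 94% or more at an unadjusted 0.05.

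These power figures are for two-sample t tests at 1.395 SD.

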
Players with musculoskeletal disorders at the time of sample selection.

Players recovering from injury.

Sample Size Calculation

A systematic probabilistic sampling of permuted blocks was carried out, for which the Epidat software, V. 4.2, was used. Taking into account the study by Sierra-Ríos et al., (2020) in which they report a mean difference of 1.13 and a standard deviation of 0.81, 5 scenarios were established to calculate the sample size (with powers of 80, 85, 90, 95 and 99%). Based on these five scenarios, the samples found are:

Scenario 1 (80% power): (20 soccer players. GE = 10 and GC = 10).

Scenario 2 (85% power): (22 soccer players. GE = 11 and GC = 11).

Scenario 3 (90% power): (24 soccer players. GE = 12 and GC = 12).

Scenario 4 (95% power): (30 soccer players. GE = 15 and GC = 15).

Scenario 5 (99% power): (40 soccer players. GE = 20 and GC = 20).

Based on these results of the calculation of different sample sizes, it decided to work with scenario 3 described above.

Randomization Process

To carry out the randomization sequence generation method, a sequence of permuted blocks of 4, 6 was generated. The relationship between groups is 1:1, for which the random assignment software (simulation) was used <https://www.sealedenvelope.com/simple-randomiser/v1/lists>.

The allocation was concealed by means of sealed and opaque envelopes, for which the 24 envelopes were available for each one of the participants. The envelopes were numbered from 1 to 24, the name of each research participant was added to them along with a sheet of carbon paper and the name of each research participant was marked for each intervention experimental group (GE) and control group (GC). This process of randomization sequence generation, allocation concealment, and allocation was performed by someone other than the research staff.

Variables

The study's variables, their operationalization, function, nature, measurement scales, units of measurement and instruments used are described in Table 1.

Table 1. Variables and their operationalization

Variable	Function	Nature	Scale	Unit of measurement/values	Instrument
PTK (Offensive IE)	Dependent	Quantitative	Discrete, interval Continuos, Ratio	Volumen (N° of times the action is performed) IE (*formula)	FOCOS
PTK (IE Defensive)	Dependent	Quantitative	Discrete, interval Continuos, Ratio	Volumen N° of times the action is performed) IE (**formula)	FOCOS

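### The analysis plan for the effectiveness indices (IE) does not say which term or visit decides the GE-GC comparison, does not adjust for pretest IE, and has a Friedman fallback with no group factor

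*Combined protocol and SAP*

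**What the plan says.** The Objectives section asks for the effect of the programme "during 12 weeks of follow-up on the PTK", expressed as offensive, defensive and global IE. Type of study sets FOCOS tests at weeks 1, 6, 11 and 16 and calls them pretest, intermediate tests 1 and 2, and posttest.

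Sample Size Calculation rests on an earlier study: "they report a mean difference of 1.13 and a standard deviation of 0.81". It lists five power scenarios and adopts the third: "Scenario 3 (90% power): (24 soccer players. GE = 12 and GC = 12"; "it decided to work with scenario 3 described above". It names no outcome, visit or test. Under Randomization Process, "The relationship between groups is 1:1".

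Analysis of data states for the IE that "a repeated measures design will be carried out that includes 4 evaluations over time", with the pretest as one of the four. The test is a repeated-measures ANOVA or, if normality fails, Friedman. A MANOVA is added without factors or hypothesis. An explicit GE versus GC comparison (independent t test or Mann-Whitney U) is written only for the executive functions, which the data collection section treats as exploratory. Confounding Bias Control lists variables to be controlled; pretest IE is not among them.

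**The concern.** The trial is sized for one between-group difference, but the IE analysis is a family of tests with no member singled out. A two-group, four-visit ANOVA yields a time effect, a group effect and a 3-df group-by-time effect, and these answer different questions:

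- The time effect is not a treatment comparison.
- The group effect averages in the pretest, where the programme cannot yet have acted.
- The interaction compares the arms, but it tests for any difference in pattern and does not estimate the difference after the full programme.

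On the Friedman route there is no group factor, so no explicit GE-GC test of the IE is stated. At stake are the power of the main conclusion and the freedom to choose the term or visit after the data are seen.

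**Working it through.** **Inputs from the documents.** Mean difference 1.13, SD 0.81, 12 per arm, allocation 1:1, alpha 0.05. Two-sided testing is taken from "two-tailed effect sizes will be reported", the only wording on sidedness.

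**Assumptions, not in the documents.** The 1.13/0.81 effect applies to IE at week 16. There is no true pretest difference. The SD is equal at all visits, with the same correlation r between any two visits, taken as 0.3, 0.5 and 0.7. There is no dropout.

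**Step 1: reproduce the plan's figure.** Standardised effect: 1.13/0.81 = 1.395. For a two-sample t test the noncentrality is 1.13/(0.81 × √(2/12)) = 1.13/0.331 = 3.42 on 22 df, which gives 90.4% power. The same method gives 10, 11, 12, 15 and 20 per arm for 80, 85, 90, 95 and 99% power, matching all five scenarios. A one-sided t test gives 8, 9, 10, 12 and 17, and a paired t test gives 7, 7, 8, 9 and 12 in one sample; neither matches. That the plan used a two-sided two-sample t test is inferred from this match.

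**Step 2: group main effect over four visits.** The SD of a player's four-visit mean is 0.81 × √((1 + 3r)/4). The averaged difference depends on how the effect builds up:
- only at week 16: 1.13 × (0+0+0+1)/4 = 0.28
- linear: 1.13 × (0+1/3+2/3+1)/4 = 0.57
- full from week 6: 1.13 × (0+1+1+1)/4 = 0.85

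Example, linear with r = 0.5: SD = 0.81 × √0.625 = 0.640; noncentrality = 0.565/(0.640 × √(2/12)) = 2.16; power 54%.

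**Step 3: group-by-time interaction.** λ = (12/2) × Σ(dₖ − d̄)²/(0.81² × (1 − r)), where dₖ is the arm difference at visit k, tested on 3 and 66 df. Linear with r = 0.5: Σ = 1.13² × 0.5556 = 0.709; λ = 6 × 0.709/0.328 = 13.0; power 85%. Effect only at week 16, or full from week 6: Σ = 1.13² × 0.75 = 0.958; λ = 17.5; power 94%.

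**Step 4: week-16 difference adjusted for pretest (ANCOVA).** Noncentrality = 1.13/(0.81 × √(1 − r²) × √(2/12)) on 21 df. At r = 0.5 this is 3.95, power 96%. It does not depend on the build-up.

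| Test | Pattern | r = 0.3 | r = 0.5 | r = 0.7 |
|---|---|---|---|---|
| Group main effect | only week 16 | 22% | 18% | 15% |
| Group main effect | linear | 66% | 54% | 46% |
| Group main effect | full from week 6 | 94% | 87% | 80% |
| Group-by-time | linear | 70% | 85% | 98% |
| Group-by-time | only week 16, or full from week 6 | 83% | 94% | 99.7% |
| Week 16 adjusted for pretest | any | about 92% | about 96% | about 99% |

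With correlation decaying over visits (AR(1), 0.7) and linear build-up, simulation gives 51% for the group effect, 82% for the interaction and 92% for the adjusted week-16 difference.

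**Step 5: time effect.** If both arms gain 1 SD linearly with no GE-GC difference (r = 0.5), the time effect is significant 99% of the time.

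**Step 6: choosing the visit afterwards.** With no effect, claiming success if any of weeks 6, 11 or 16 separates the arms at 0.05 gives 11-14% false positives in simulation. Three independent tests would give 1 − 0.95³ = 14.3%.

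**The case against.** A reader might infer that this ANOVA cannot compare the arms. That goes too far. The group-by-time interaction is a valid randomised comparison of change, and having the pretest as a level is what makes it one; the pretest dilutes only the group main effect.

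A reader might also infer that the trial is underpowered. The documents do not support that as a general statement. The interaction passes 90% in several settings. Analysis of data itself says "with alpha (α) set to 0.05 and statistical power 0.8 (1- β", and the interaction falls short of 0.8 only for linear build-up at r = 0.3. The 0.8 and the adopted 90% should in any case be reconciled.

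Nor do the visits stand as equals. The intermediate and posttest labels, and the full battery at weeks 1 and 16 only, point to week 16 as the end point. The 11-14% describes a pick-any-visit procedure that the plan does not state.

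Finally, placing 1.13/0.81 on IE at week 16 is an assumption. Offensive and defensive IE are averages of success proportions and cannot exceed 1, so 1.13 cannot be a raw difference in either.

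All of this stands as a limit on the claim. None of it supplies what is missing. The labels set no decision rule, the interaction is never named as deciding, and the MANOVA has no stated factors to fill the gap on the Friedman route.

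**Conclusion.** The point holds as under-specification of the main comparison, not as a wrong method. The plan does not say which term or visit decides the GE-GC comparison of the IE, does not adjust for pretest IE, and on the Friedman route states no explicit between-arm test. The 90% belongs to a single two-group difference that the IE analysis never specifies.

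Under the assumptions above, power for the candidate between-arm terms runs from 15% (group effect, benefit only at week 16, r = 0.7) to 99.7% (interaction, r = 0.7). The pretest-adjusted week-16 difference stays at about 92% or more for the three correlations, whatever the build-up. These figures rest on the assumed visit correlation and on carrying 1.395 SD over to IE at week 16. The 11-14% is a worst-case reading and should not be quoted as the plan's error rate.

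**What to change.** In Analysis of data:

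1. Define the programme effect as the GE-GC difference at week 16 (posttest) in one named IE. Global IE is a natural candidate, since the FOCOS section says it represents the PTK.
2. Estimate it by ANCOVA with pretest IE as covariate, or by a mixed model on weeks 6, 11 and 16 with arm, visit, arm-by-visit and pretest IE.
3. Report weeks 6 and 11 and the other indices as secondary.
4. Replace the Friedman fallback with a between-group method, for example a rank-based or permutation version of the same contrast.
5. State that no treatment conclusion will be drawn from the time or group main effect.
6. Reconcile the two power figures (0.8 and 90%).

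The cost is SAP wording and one degree of freedom (21 instead of 22). No visit or measurement is added, because pretest IE is already in the schedule. The change should be made before the outcome data are examined by arm.
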